**Table 10: Immune-Related Adverse Events (Preferred Terms)**

Pneumonitis		
Acute interstitial pneumonitis	Interstitial lung disease	Pneumonitis
Colitis		
Intestinal obstruction	Colitis	Colitis microscopic
Enterocolitis	Enterocolitis hemorrhagic	Gastrointestinal perforation
Necrotizing colitis	Diarrhea	
Endocrine		
Adrenal insufficiency	Hyperthyroidism	Hypophysitis
Hypopituitarism	Hypothyroidism	Thyroid disorder
Thyroiditis		
Hematologic		
Autoimmune hemolytic anemia	Aplastic anemia	Thrombotic thrombocytopenic purpura
Idiopathic (or immune) thrombocytopenia purpura	Disseminated intravascular coagulation	Hemolytic uremic syndrome
Any Grade 4 anemia regardless of underlying mechanism		
Hepatic		
Hepatitis	Autoimmune hepatitis	Transaminase elevations
Infusion Reactions		
Allergic reaction	Anaphylaxis	Cytokine release syndrome
Serum sickness	Infusion reactions	Infusion-like reactions
Neurologic		
Autoimmune neuropathy	Guillain-Barre syndrome	Demyelinating polyneuropathy
Myasthenic syndrome		
Ocular		
Uveitis	Iritis	
Renal		
Nephritis	Nephritis autoimmune	Renal failure
Renal failure acute	Creatinine elevations (report as event of clinical interest if $\geq$ Grade 3 or any grade resulting in dose modification or use of systemic steroids to treat the AE)	
Skin		
Dermatitis exfoliative	Erythema multiforme	Pruritus
Rash	Rash generalized	Rash maculo-papular
Stevens-Johnson syndrome	Toxic epidermal necrolysis	
Any rash considered clinically significant in the physician's judgment		
Other		
Myocarditis	Pancreatitis	Pericarditis
Any other Grade 3 event which is considered immune-related by the physician		

### 8.3. Clinical Laboratory Tests

#### 8.3.1. Laboratory Value Definitions

Laboratory values and change from baseline values will be summarized descriptively by visit. The baseline value will be determined using the last nonmissing values collected prior the first dose. For baseline laboratory candidates with the same date and time, additional rules may be provided after consultation with the medical monitor to delineate which value will be defined as baseline.

Laboratory test values outside the normal range will be assessed for severity based on CTCAE grade or similar criteria where clinical intervention is required for CTCAE grading. See [Appendix B](#) for laboratory grading criteria. The incidence of abnormal laboratory values and shift tables relative to baseline will be tabulated.

#### 8.3.2. Laboratory Value Summaries

Clinical laboratory tests, including hematology and serum chemistry (see [Appendix A](#)), will be performed for each subject during the study in accordance with [Table 6](#).

If specific safety issues arise, additional unscheduled laboratory tests/analyses may be performed at the discretion of the investigator.

All test results and associated normal ranges from central laboratories will be reported in International System of Units (SI). All tests with numeric values will have a unique unit per test. Any laboratory test results and associated normal ranges from local laboratories will be converted to SI units. For the limited number of cases where the associated normal ranges from a local laboratory cannot be obtained despite due diligence, a set of standard normal ranges based on documented reference ranges will be applied to facilitate reporting the test results.

When there are multiple nonmissing laboratory values for a subject's particular test within a visit window, the convention shown in [Table 11](#) will be used to determine the record used for by-visit tabulations and summaries.

**Table 11: Identification of Records for By-Visit Summaries**

Priority	Laboratory Visit	Proximity to Visit Window	Tiebreaker
1	Scheduled	In-window	Use smallest laboratory sequence number
2	Unscheduled	In-window	
3	Scheduled	Out-of-window	

Laboratory parameters identified in [Appendix A](#) will be summarized. Shift tables based on worst postbaseline value recorded will use all postbaseline values. Other laboratory parameters collected will only be listed in an appendix to the Clinical Study Report (CSR) in their original units without SI conversions.

Numeric laboratory values will be summarized descriptively, and non-numeric test values will be tabulated. In addition, line graph and box-and-whisker plots will be provided for prespecified laboratory parameters.

For test results that will be summarized with available normal ranges, the number and percentage of subjects with the laboratory values being low (but never high), normal, high (but never low), and both low and high will be calculated for each test.

This shift summary will be produced for each test for the safety population as well as the subset of subjects treated at the MTD. The denominator for the percentage calculation will use the number of subjects in the baseline category (ie, low, high, normal, missing) as the denominator for the percentage in each of the categories during the treatment period.

For all gradable laboratory parameters identified in [Appendix A](#), the values will be classified into grade levels corresponding to CTCAE v4.03 criteria. For specific laboratory values requiring clinical intervention to grade, the classification according to the quantitative component will be provided. See [Appendix B](#) for laboratory grading criteria.

The number and percentage of subjects with the laboratory values of Grade 1, 2, 3, or 4 will be calculated for each treatment according to the largest treatment-emergent worsening of laboratory grade. Separate summaries for abnormally high and abnormally low laboratory values will be provided when the laboratory in question has both high and low grading criteria. For instance, if a subject has a baseline fasting glucose of 210 mg/dL, maximum fasting glucose after starting treatment of 245 mg/dL, and minimum fasting glucose after starting treatment of 52 mg/dL, then the subject should be reported as follows:

- The subject will be counted as a Grade 2 "Glucose decreased" in summaries of hypoglycemia because the subject was not hypoglycemic at study entry but became hypoglycemic after treatment.
- The subject will not count as a "Glucose increased" in summaries of hyperglycemia because the subject met the numeric requirements for Grade 2 hyperglycemia at baseline (fasting glucose value > 160 to 250 mg/dL) and did not increase in grade after starting treatment.

In cases where differentials of hematology parameters are obtained without corresponding absolute count data, efforts will be made to investigate if the conversion to an absolute value will lead to additional abnormalities. This will be discussed with the clinical team regarding appropriate documentation and action.

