6. STUDY ASSESSMENTS

All study assessments will be performed as indicated in the schedule of assessments (see [Table 24](#)) and laboratory assessments (see [Table 25](#)). The required analytes for each laboratory test are shown in [Table 26](#). The order of assessments is suggested by the order of mention within the schedule of assessments.

Table 24: Schedule of Assessments

Visit (Range)	Screening Days -28 to -1	Treatment Cycles					EOT	Follow-Up	
		C1D1	C1D8	C2D1	Day 1 All Subsequent Cycles	Every 12 Weeks	Discontinuation	Safety Follow-Up Visit 1	Safety Follow-Up Visit 2
		±3 Days	±3 Days	±3 Days	±3 Days	±5 Days	+ 7 Days After Last Dose	42 Days After EOT ±7 Days	90 Days After EOT ±7 Days
Administrative procedures									
Informed consent	X								
Inclusion/exclusion criteria	X	X							
Medical and cancer history	X								
Smoking history	X								
Prior/concomitant medications review	X	X		X	X				
Administer epacadostat at clinic		X	X ^a	X					
Administer durvalumab		X		X	X				
Poststudy anticancer therapy status								X	X
Survival status									
Clinical procedures and assessments									
Comprehensive physical exam	X						X	X	X
Targeted physical exam		X		X	X				
Vital signs and weight (height at screening only)	X	X		X	X		X		
Postinfusion observation ^b		X							
12-lead ECG	X	X ^c		X ^c			X	X	X
Adverse event assessment ^d	X	X		X	X		X	X	X
Laboratory assessments	X	X ^e	X ^f	X	X ^e	X	X	X	X
Chest radiograph	X								
Tumor tissue collection ^g	X			X ^h					
Tumor imaging	X					X ⁱ	X ^j		

C1D1 = Cycle 1 Day 1; C1D8 = Cycle 1 Day 8; C2D1 = Cycle 2 Day 1.

^a **Phase 1 Subjects Only:** Administer epacadostat in clinic on C1D8 when PK assessment is performed.

^b Patients will be observed in clinic for 3 hours after the first infusion of durvalumab is administered.

^c ECGs should be performed on Cycle 1 Day 1 and Cycle 2 Day 1 before epacadostat and durvalumab administration and 1 and 2 hours after administration of epacadostat.

See Table 27 for details regarding specific timing of ECGs.

^d Subjects need to be followed for AEs for 90 days after the last dose of durvalumab or epacadostat (whichever comes later).

^e If LFTs are abnormal, then LFT monitoring should increase to twice per week until resolved to baseline.

^f **Phase 1 Subjects Only:** Pharmacokinetic samples are collected at Cycle 1 Day 8.

^g If subject agrees to such in the ICF, any leftover tissue will be stored for future biomedical research.

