6.4. Follow-Up Period

6.4.1. Safety Follow-Up

The safety follow-up period is the interval between the EOT visit and the last scheduled safety follow-up visit, which should occur 90 days after the EOT visit (or after the last dose of study drug if the EOT visit was not performed). Safety follow-up visit 1 will be performed 42 days (± 7 days) after the EOT visit or the last dose of study treatment (if the EOT visit was not performed). Safety follow-up visit 2 will be performed 90 days (± 7 days) after the EOT visit or last dose of study treatment (if the EOT visit was not performed). Adverse events and SAEs must be reported up until at least 90 days after the last dose of study treatment or until study drug-related toxicities resolve, return to baseline, or are deemed irreversible, whichever is longer. Reasonable efforts should be made to have the subject return for the safety follow-up visits and report any AEs that may occur during this phase.

If a subject initiates a new anticancer therapy within 90 days after the last dose of study treatment, reasonable efforts should be made to conduct the next scheduled safety follow-up (42-day or 90-day) visit before the first dose of the new therapy.

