#### **4.1.5. Last Available Value**

The last available value is the last nonmissing measurement obtained after starting INCB024360 or MEDI4736 and within 90 days after the last dose of INCB024360 or MEDI4736.

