### 8.2. Adverse Events

#### 8.2.1. Adverse Event Definitions

A treatment-emergent adverse event (TEAE) is any AE either reported for the first time or worsening of a pre-existing event after first dose of study drug. Analysis of AEs (as discussed below) will be limited to TEAEs, but data listings will include all AEs regardless of their timing to study drug administration.

Adverse Events will be tabulated by the MedDRA preferred term and system organ class. Severity of AEs will be described and graded using the National Cancer Institute Common Terminology Criteria for Adverse Events (CTCAE) v4.03. The CTCAE reporting guidelines and grading details are available on the Cancer Therapy Evaluation Program website.

A grading (severity) scale is provided for each AE term. If the toxicity is not included in the CTCAE v4.03 criteria, it will be rated on a scale of 1 to 4 as follows: 1 = mild, 2 = moderate, 3 = severe, and 4 = life threatening. All toxicities will be graded based on the worst level reached, not the level they may have reached if they had not been treated. When the intensity of

an AE changes over time for a reporting period (eg, between visits), each change in intensity will be reported as an AE until the event resolves.

The subset of AEs considered by the investigator to be related to INCB024360 or MEDI4736 will be considered to be treatment-related AEs. If the investigator does not specify the relationship of the AE to study drug, the AE will be considered to be treatment related. The incidence of AEs and treatment-related AEs will be tabulated. Serious adverse events (SAEs) will also be tabulated.

Any missing onset date, causality, or severity must be queried for resolution. Unsolved missing values will be handled according to the following rules:

- An unsolved missing causality will be considered treatment related.
- An unsolved missing severity will be identified as an unknown severity.

For purposes of analysis, all AEs will be considered TEAEs unless the AE can unequivocally be defined as not treatment emergent. Therefore, an unsolved missing onset date will be considered treatment emergent, with the following exceptions:

- If the stop/resolution date is before the first dose administration date on Day 1, then the AE will be considered as not being treatment emergent.

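### The worst-grade laboratory shift tables have no cut-off at new anticancer therapy, so follow-up values drawn on a later treatment can be counted as the worst grade

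*SAP*

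**What the plan says.** The rule for worst-value tables is in SAP 8.3.2, below Table 11: "Shift tables based on worst postbaseline value recorded will use all postbaseline values". The graded summary in the same section counts subjects "according to the largest treatment-emergent worsening of laboratory grade", with no end date for laboratory data. For the low/normal/high summary, the section makes the baseline category the "denominator for the percentage in each of the categories during the treatment period".

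SAP Appendix C plans the shift tables as 3.3.5.1 and 3.3.5.2 (tests graded in one direction) and 3.3.6.1 and 3.3.6.2 (two directions). All four are titled as shifts in CTC grade to the worst abnormal value. The 3.3.5 pair is marked for the body of the study report.

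Protocol Table 25 and SAP Table 6 schedule chemistry, liver and hematology panels at safety follow-up visits 1 and 2. Protocol 6.4.1 foresees new treatment in that period: "If a subject initiates a new anticancer therapy within 90 days after the last dose of study treatment", the site should make reasonable efforts to hold the next scheduled follow-up visit before the first new dose. Protocol Table 24 collects "Poststudy anticancer therapy status" at both visits.

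Two other SAP rules do set an end. Table 8 censors PFS when new anticancer treatment starts. Section 4.1.5 limits the last available value to measurements "within 90 days after the last dose of INCB024360 or MEDI4736". A treatment-emergent AE (SAP 8.2.1) is "any AE either reported for the first time or worsening of a pre-existing event after first dose of study drug", with no end stated. The SAP has one version, dated 26 NOV 2014, and its section 2.1 keeps it in force for later amendments unless it is superseded.

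**The concern.** A worst-value table is sensitive to a single draw. If that draw is taken after the subject has moved to another anticancer drug, its grade enters a table headed by the study-treatment group. Protocol 9.4.4 names hemoglobin, neutrophils and platelets as key parameters to be graded, and cytotoxic treatment would be expected to depress these.

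Laboratory evaluations are part of the Phase 1 primary and Phase 2 secondary safety endpoints. The tables at issue will be read as the laboratory safety profile of the combination, some of them in the body of the report.

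**Working it through.** The plan gives no figure to reproduce. The check is of which values the rule admits, and when.

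**1. Latest scheduled laboratory day after last dose**
- The EOT visit falls 0 to 7 days after last dose (Protocol 6.3).
- Visit 2 falls 90 ± 7 days after EOT (Protocol 6.4.1).
- Earliest: 0 + 90 − 7 = 83 days. Latest: 7 + 90 + 7 = 104 days.
- Scheduled values pass day 90 by at most 104 − 90 = 14 days. Unscheduled tests, which SAP 8.3.2 allows, could be later.

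**2. Can a value on new therapy enter when the site complies fully?**
The request in Protocol 6.4.1 covers only the next scheduled visit.
- New therapy starts after visit 1: the next visit is visit 2. If it is brought forward successfully, no scheduled value is affected.
- New therapy starts before visit 1: visit 1 is brought forward, but visit 2 is not waived. Take a start 30 days after EOT as an illustration. Visit 2 falls on days 83 to 97 after EOT, which is 83 − 30 = 53 to 97 − 30 = 67 days into the new therapy.
- Reasonable efforts fail: either visit can be affected.

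**3. Direction**
The worst of a larger set of values is at least as bad as the worst of a subset of it. Admitting later values can leave a grade unchanged or raise it, but never lower it.

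**4. Size**
Added subjects in a grade row = n × (share with a draw after new therapy) × (share of those whose grade at that draw exceeds their own earlier worst). The documents give n, for example 28 in each 300 mg BID expansion cohort (Protocol Table 6), and neither share. One such subject is 1/28 = 3.6 percentage points if all 28 form the denominator.

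**5. One window or two?**
The shift rule says all postbaseline values; the low/normal/high sentence says the treatment period. Protocol 4.1 separates the treatment period from follow-up, so the first includes visits 1 and 2 and the second excludes them. Appendix C lists no low/normal/high shift table, so the planned tables are the CTC-grade ones under the open-ended rule. A programmer could still apply either window.

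**The case against.** The strongest reply is that little turns on these tables. The MTD rests on DLTs within 42 days of first dose. The Phase 2 suspension rule (Protocol 9.6) counts AEs attributed to the study drugs. There is no control arm, and any error overstates toxicity, which is the cautious direction. By-visit summaries and full laboratory listings would let a careful reader find follow-up values. Stopping at new therapy also has a price, because Protocol 5.6.3 warns that immune-related events can appear several months after the last dose.

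Most of this stands as a limit on the consequences. No dose or enrollment decision depends on the shift tables. It does not make the rule sound, since a reader of an in-text worst-grade table cannot tell which grades came after a new drug was started.

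Four stronger readings are tempting, and the documents do not support them:
- **A reader might infer that chemotherapy toxicity is reported as caused by study drug.** Shift tables assign no causality. Relatedness is an investigator judgement on AEs and has its own tables.
- **A reader might put a percentage on the inflation, or say that it differs between cohorts.** Neither share in the size formula is given. New therapy need not be cytotoxic, some subjects will already have had a high grade on study, and Protocol 6.4.1 removes part of the exposure.
- **A reader might see a contradiction with the 90-day limit in SAP 4.1.5.** That limit defines a different quantity, and for scheduled data the difference is at most 14 days.
- **A reader might call the TEAE definition unbounded.** AE collection runs to 90 days after last dose and beyond that mainly for unresolved drug-related toxicity, so collection largely bounds it. Only the missing stop at new therapy remains.

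**Conclusion.** The point holds in a limited form. The CTC-grade worst-value shift tables admit laboratory values taken after new anticancer therapy, and full compliance with Protocol 6.4.1 does not prevent this for subjects who start before visit 1. The effect can only raise grades. Its size is unknown and could be nil in a given cohort; each affected subject moves a row of a 28-subject cohort by 3.6 percentage points. SAP 8.3.2 is also inconsistent about whether follow-up values belong in its shift summaries. The missing 90-day limit is minor. This rests on the text of the two documents and assumes that some subjects start new therapy before visit 2, which the protocol itself anticipates. It should be corrected in the SAP, but it does not threaten the dose selection or the response-rate endpoint.

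**What to change.** In SAP 8.3.2, define one laboratory analysis window: first dose through the earlier of (a) 90 days after the last dose of either drug, counted from whichever drug stopped later, and (b) the day before the first dose of new anticancer therapy. Apply it to the shift tables and the CTCAE-grade summaries. Replace both the all-postbaseline wording and the treatment-period wording with a reference to it. List later values with a flag.

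Add the same new-therapy end to the TEAE definition in SAP 8.2.1. Report immune-related AEs and treatment-related SAEs over the full 90 days as a separate line, so that delayed immune toxicity stays visible.

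The cost is SAP wording and one derivation. It needs the start date of the new therapy. Protocol Table 24 shows that therapy status is collected at both follow-up visits; that the CRF also records the date is an assumption, since the CRF is not shown.

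There are two small losses. Late immune-related laboratory changes after new therapy move from the tables to the listing. So do visit 2 values drawn on days 91 to 104 after last dose, even without new therapy. If the sponsor wants to keep the latter, limit (a) can be set at visit 2 with its window; the stop at new therapy is the essential part.

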#### **8.4. Vital Signs**

Vital signs, including systolic blood pressure, diastolic blood pressure, heart rate, respiration rate, and body temperature, will be taken with subjects in the seated position during the study in accordance with [Table 5](#). Change and percentage change from baseline will be calculated using the last nonmissing value before first dose of study drug (Day 1) as the baseline value.

Incidences of clinically notable vital sign abnormalities are defined in [Table 12](#). The abnormal values for subjects exhibiting clinically notable vital sign abnormalities will be listed along with their assigned treatment group. Alert vital signs are defined as an absolute value outside the defined range and percentage change greater than 25%.

**Table 12: Criteria for Clinically Notable Vital Sign Abnormalities**

Parameter	High Threshold	Low Threshold
Systolic blood pressure	> 155 mmHg	< 85 mmHg
Diastolic blood pressure	> 100 mmHg	< 40 mmHg
Heart rate	> 100 bpm	< 45 bpm
Temperature	> 38°C	< 35.5°C
Respiratory rate	> 24/min	< 8/min

## 8.5. Electrocardiograms

Twelve-lead ECGs will be obtained for each subject during the study in accordance with [Table 5](#). Electrocardiogram results will be reviewed for clinically notable abnormalities according to predefined criteria (see [Table 13](#)). Electrocardiogram abnormalities, both at baseline and postbaseline visits, will be tabulated by treatment group. Incidences of abnormalities will be listed with study visit, assigned treatment group, and a description of the abnormality.

**Table 13: Criteria for Clinically Notable ECG Abnormalities**

Parameter	High Threshold	Low Threshold
QTcF a	> 460 ms	< 295 ms
PR	> 220 ms	< 75 ms
QRS	> 120 ms	< 50 ms
QT	> 500 ms	< 300 ms
RR	> 1500 ms	< 600 ms

a QTcF (Fridericia correction).

## 9. INTERIM ANALYSES

### 9.1. Overview of Interim Analysis

No interim analysis for efficacy or futility will be conducted in this study. As this Phase 1/2 study is intended to support a Phase 3 development decision, the selected Type I and Type II error rates lead to a relatively small sample size in this Protocol. As such, the level of uncertainty for point estimates at an interim analysis limits the value of such an interim analysis. The safety of subject participants will be assessed through regular meetings between investigators and sponsors who will monitor for critical safety signals.

### 9.2. Guidelines for Decision Rules

An interim safety analysis is planned for Phase 2 after 16 subjects have been enrolled and treated for 8 weeks, and then every 3 months thereafter. If either of the following is reported during

these reviews, enrollment of subjects would be suspended until the sponsor determined the appropriate course of action and notified IRBs and regulatory authorities:

- $\geq 40\%$  of subjects report a DLT or
- $\geq 20\%$  of subjects have had a nondermatologic immune-related AE  $\geq$  Grade 3 that was attributable to the investigational agent.

Based on these rules, the probabilities of stopping a treatment group for safety is provided in [Table 14](#).

